7.11 Day 90 Assessment

Type of Assessment: In-person at investigational site required; remote only for documented COVID-19 related disruption.
Window: 90 ± 14 Days
If a COVID-19-related disruption prevents an in-person assessment within window: 
As much data as possible may be collected remotely.The absence of a 12-lead ECG during a remote assessment is not a protocol deviation.If a radiologic examination is required due to prior diminished phrenic nerve response, an inspiration / expiration chest X-ray (CXR) performed in-person or at another healthcare site may be substituted.
AAD Treatment: During the Blanking Period the subject should be assessed for AAD continuation. At Investigator discretion, Class I / III AADs may be stopped to allow assessment of the subject's potential for off-drug freedom from recurrent AF, AFL, or AT. Subjects who require continued AAD treatment may be continued; preferably with a Failed AAD . Using a Non-Failed AAD or amiodarone would create an unnecessary Treatment Failure.

Subjects will be assessed at Day 90 ± 14 days following the Index Procedure / Rescheduled Index Procedure. Study data will be collected at the Day 90 Assessment including but not limited to:

- Adverse events
- Data regarding the use, changes in or discontinuation of anticoagulation, rate control and / or AADs
- Recurrent arrhythmia, cardioversions, ablations, or hospital admissions since last assessment
- Site staff will confirm ICM programming and successful LATITUDE Clarity transmissions since last assessment
 - Assess for any recurrence of AF/AFL/AT
 - Any reported AFL recurrence will require a 12-lead ECG for ACL adjudication
 - Confirm ICM programming parameters
 - Any programming outside of the defined nominal parameters (Section 7.6) prior to a confirmed recurrence of Detectable AF, AT or AFL must be entered into the EDC and justification provided.
 - ICM may be reprogrammed, as needed, to facilitate appropriate arrhythmia identification and investigator notification after the subject experiences a confirmed recurrence of Detectable AF, AT or AFL.
- Cardiac rhythm as determined by a 12-lead ECG at the time of the assessment (in-person assessment only). All 12-lead ECGs for Treatment Subjects will be provided to the Arrhythmia Core Laboratory (ACL).
- If the post-Index Procedure / Rescheduled Index Procedure fluoroscopy indicated diminished phrenic nerve response and resolution has not been previously demonstrated, complete a radiologic examination of the diaphragm
- If there is a clinical suspicion of PV stenosis, a cardiac CT or MRI scan of the same type as the baseline scan to assess the dimensions of the PVs.
- If data is collected remotely, the date, time and communication method(s) used to collect the data remotely.

7.12 Day 180 Assessment

Type of Assessment: Remote; In-person allowed
Window: 180 ± 30 Days
If a COVID-19-related disruption interferes with the performance of this assessment, as much data as possible may be collected remotely, in or out of window.

Subjects will be assessed remotely at Day 180 ± 30 days following the Index Procedure / Rescheduled Index Procedure. Any subject who is hospitalized or seen in the office as standard of care at the time of the assessment may have their Day 180 assessment performed in-person.

Study data will be collected at the Day 180 Assessment including but not limited to:

- Adverse events
- Data regarding the use, changes in or discontinuation of anticoagulation, rate control and / or AADs
- Recurrent arrhythmia, cardioversions, ablations, or hospital admissions since last assessment
- Site staff will confirm ICM programming and successful LATITUDE Clarity transmissions since last assessment
 - Assess for any recurrence of AF/AFL/AT
 - Any reported AFL recurrence will require a 12-lead ECG for ACL adjudication
 - If the investigator determines that the subject has experienced the first recurrence after the blanking period of Detectable AF, AFL or AT, upload documentation to EDC
 - Confirm ICM programming parameters
 - Any programming outside of the defined nominal parameters (Section 7.6) prior to a confirmed recurrence of Detectable AF, AT or AFL must be entered into the EDC and justification provided.
 - ICM may be reprogrammed, as needed, to facilitate appropriate arrhythmia identification and investigator notification after the subject experiences a confirmed recurrence of Detectable AF, AT or AFL.
- Quality of Life Measures:
 - The 3-level EuroQol standardized questionnaire of health states (EQ-5D-3L) The Atrial Fibrillation Effect on QualiTy-of-Life Questionnaire (AFEQT) quality of life assessments
- The date, time and communication method(s) used to collect the data remotely.

7.13 Day 360 Assessment

Type of Assessment: In-person at investigational site required; remote only for documented COVID-19 related disruption.
Window: 360 ± 30 Days
If a COVID-19-related disruption interferes with the performance of this assessment: 
 • As much data as possible may be collected remotely, in or out of window. • The absence of a 12-lead ECG during a remote assessment is not a protocol deviation.

- If a radiologic examination is required due to prior diminished phrenic nerve response, an inspiration / expiration chest X-ray (CXR) performed in-person or at another healthcare site may be substituted.

Subjects will be assessed at 360 days ± 30 days following the Index Procedure / Rescheduled Index Procedure.

Study data will be collected at the Day 360 Assessment including but not limited to:

- Adverse events
- Data regarding the use, changes in or discontinuation of anticoagulation, rate control and / or AADs
- Recurrent arrhythmia, cardioversions, ablations, or hospital admissions since last assessment
- Site staff will confirm ICM programming and successful LATITUDE Clarity transmissions since last assessment
 - Assess for any recurrence of AF/AFL/AT
 - Any reported AFL recurrence will require a 12-lead ECG for ACL adjudication
 - If the investigator determines that the subject has experienced the first recurrence after the blanking period of Detectable AF, AFL or AT, upload documentation to EDC
 - Confirm ICM programming parameters
 - Any programming outside of the defined nominal parameters (Section 7.6) prior to a confirmed recurrence of Detectable AF, AT or AFL must be entered into the EDC and justification provided.
 - ICM may be reprogrammed, as needed, to facilitate appropriate arrhythmia identification and investigator notification after the subject experiences a confirmed recurrence of Detectable AF, AT or AFL.
- If the post-Index Procedure / Rescheduled Index Procedure fluoroscopy indicated diminished phrenic nerve response and resolution has not been previously demonstrated, complete a radiologic examination of the diaphragm
- If there is a new clinical suspicion of PV stenosis, a cardiac CT or MRI scan of the same type as the baseline scan to assess the dimensions of the PVs.
- Cardiac rhythm as determined by a 12-lead ECG at the time of the assessment (in-person assessment only). All 12-lead ECGs for Treatment subjects will be provided to the ACL.
- Quality of Life Measures:
 - The 3-level EuroQol standardized questionnaire of health states (EQ-5D-3L)
 - The Atrial Fibrillation Effect on QualiTy-of-Life Questionnaire (AFEQT) quality of life assessments
- If data is collected remotely, the date, time and communication method(s) used to collect the data remotely

At the completion of all components of the Day 360 Assessment a Study Exit CRF will be completed.

7.14 Re-Ablation Procedures

7.14.1 Re-Ablation Procedure within the Blanking Period

For subjects undergoing a first re-ablation procedure within the Blanking Period for Detectable AF, AFL or AT, the procedure will be performed by the investigator under the procedures and data

requirements of **Section 7.7.1**, modified to assess and treat only those locations required, and including the pre- and post-procedure NIHSS.

The FARAPoint PFA Catheter will not be utilized for any re-ablation procedure. If repeat ablation is required for CTI-mediated flutter, any commercially available BSC RF catheter will be used. Such re-ablation using the methods and devices described in **Section 7.7.1** does not constitute a Treatment Failure.

7.14.2 Other Re-Ablation Procedures

For a second re-ablation during the Blanking Period and for any re-ablation after the Blanking Period, any commercially available ablation catheter will be used for re-ablation.

The FARAPULSE Pulsed Field Ablation System is not permitted to be used for these procedures.

Such re-ablations constitute Treatment Failures, and therefore during such procedures other sites may be ablated at Investigator discretion.

The following data will be collected for these procedures:

- Adverse events
- During re-ablation procedures, a mapping procedure will be performed to characterize the reconnection status for each originally treated PV and the PW (if a left-sided re-ablation), and the CTI, to characterize lesion durability.
- Limited ablation data.

7.15 Unscheduled Assessments

Type of Assessment: Either remote or in-person at investigational site.

Any unscheduled follow-up assessments for cardiovascular events that occur throughout study follow-up will be documented. Study data will be collected including but not limited to:

- Adverse events
- Data regarding the use, changes in or discontinuation of anticoagulation, rate control and / or AADs
- Recurrent arrhythmia, cardioversions, ablations, or hospital admissions since last assessment
- Site staff will confirm ICM programming and successful LATITUDE Clarity transmissions since last assessment
 - Assess for any recurrence of AF/AFL/AT
 - Any reported AFL recurrence will require a 12-lead ECG for ACL adjudication
 - If the investigator determines that the subject has experienced the first recurrence after the blanking period of Detectable AF, AFL or AT, upload documentation to EDC
 - Confirm ICM programming parameters
 - Any programming outside of the defined nominal parameters (Section 7.6) prior to a confirmed recurrence of Detectable AF, AT or AFL must be entered into the EDC and justification provided.

- ICM may be reprogrammed, as needed, to facilitate appropriate arrhythmia identification and investigator notification after the subject experiences a confirmed recurrence of Detectable AF, AT or AFL.
- Cardiac rhythm documentation:
 - At the investigational site: 12-lead ECGs will be collected and provided to the ACL.
 - At another health care site: a record of any ECG should be obtained if available.
 - Remote, not at a health care site: An LUX-Dx manual transmission should be requested.
- If there is a new clinical suspicion of PV stenosis, a cardiac CT or MRI scan of the same type as the baseline scan to assess the dimensions of the PVs.
- If data is collected remotely, the date, time and communication method(s) used to collect the data remotely.

7.16 Unforeseen Circumstances

There may be unforeseen circumstances that occur during the course of the study, such as a natural disaster or a global pandemic (e.g., COVID-19) that prevents a subject from participating in study assessments during the required follow-up window. While every attempt should be made to avoid disruptions in collecting study data, it is important to collect as much data as possible, by any available means and from any available resources. This may include obtaining records from an outside clinic, hospital or other healthcare facility that is not IRB / EC / REB approved.

In the event that study data must be collected remotely, every effort should be made to collect the data within the study assessment window. Critical data collected during the study includes any device or procedure-related adverse events, recurrence of any AF / AT / AFL, and a Cardiac CT or MRI (if PV stenosis is suspected). The LUX-Dx will continue to be used to assess the subjects' heart rhythm. If a Cardiac CT or MRI is required because PV stenosis is suspected, the Cardiac CT or MRI – preferably using the baseline modality – may be performed at another healthcare facility and the window to conduct this test may be extended by up to one month (30 days) following the normal study assessment window.

When such unforeseen circumstances result in a deviation from the requirements of the protocol, the deviations will be distinguished from routine protocol deviations and reported separately.

7.17 Study Completion

Each Roll-In Subject and Treatment Subject will be followed until the Day 360 Assessment. Participation in the study is considered complete upon completion of the Day 360 Assessment. Each Attempt Subject will be followed through the Day 30 Assessment following the Index Procedure / Rescheduled Index Procedure and then exited from the study. In case of premature termination of the study, please refer to **Section 20.1** of the Phase 1 ADVANTAGE AF clinical investigational plan.

Following termination or completion of the study, subjects will be managed according to local institution practice. Sites will need to document and complete the "End of Study" CRF to signify study completion.

7.18 Source Documents

It is preferable that original source documents are maintained, when available. In lieu of original source documents, certified copies are required to be maintained. A certified copy is a copy (irrespective of the type of media used) of the original record that has been verified (i.e., by a dated signature or by generation through a validated process) to have the same information, including data that describe the

context, content, and structure, as the original. Source documentation includes but is not limited to those items noted in **Table 7.18-1** below.

Table 7.18-1: Source Documentation Requirements

Requirement	Disposition
Screening and enrollment log	Retain at Center
Informed consent documentation process	Retain at Center
Medical history documents pertaining to eligibility criteria	Retain at Center
Documentation of demographics data	Retain at Center
Pregnancy testing, if applicable	Retain at Center
Required laboratory testing	Retain at Center
Cardiovascular / pulmonary examination	Retain at Center
Procedural Medications Administered, AADs, and Anticoagulation Medication Regimen and Changes	Retain at Center
Medical history	Retain at Center
Quality of Life Instruments (AFEQT and EQ-5D-3L)	Retain at Center
NIH Stroke Scale Assessments	Retain original at center and submit copies and copies of all associated source documents if an increase in scale is observed from baseline
If determined necessary, neurological consultation and brain MRI (DW-MRI)	Retain originals at center and submit copies of all source documents and copy of complete scan to BSC
Baseline cardiac imaging and any required follow-up imaging	Retain at Center
LUX-Dx insertion details and arrhythmia recurrence recordings	Retain insertion data at Center and Upload recurrence data to BSC EDC
12-Lead ECGs data including ongoing rhythm	Retain at Center Submit copies of the ECGs collected at Day 90 and Day 360 Follow up, from LUX-Dx detected AFL recurrence, and Unscheduled visits when applicable to the ACL.
Post-ablation electrograms showing entrance block for each treated PV	Retain at Center (Submit to BSC if Rhythmia)
Post-ablation electrogram documentation demonstrating PWI	Retain at Center (Submit to BSC if Rhythmia)
Post-ablation electrograms showing bidirectional isthmus block (CTI ablations only)	Retain at Center (Submit to BSC if Rhythmia)
Recording lab logs, showing PV entrance block, PW isolation and CTI BDB (if applicable)	Retain at Center
Signed Technical Source Form	Retain at Center
Printed EP Lab Procedure Report	Retain at Center

Requirement	Disposition
Adverse Events	Retain at Center, copy may be requested by BSC
In the event of a patient death: 
 • Death narrative • Relevant medical records • Death Certificate • Autopsy report 	Submit one copy to BSC, Retain one copy at center
For events adjudicated by CEC: 
 • Relevant medical records 	Submit one copy to BSC, Retain one copy at center

7.19 Local Laboratory Documentation

Normal values for the required blood tests for each participating laboratory will be collected for each study site. Appropriate certifications and documentation records are required to be maintained at the site for participating laboratories.

8 Statistical Considerations

8.1 Endpoints

The ADVANTAGE AF Phase 2 Study has endpoints designed to assess the safety and effectiveness of the FARAPULSE PFA System for treatment of drug resistant, symptomatic persistent atrial fibrillation using the FARAWAVE Catheter, and when applicable using the FARAPPOINT Catheter for the CTI-mediated atrial flutter as an adjunctive use.

8.1.1 Primary Safety Endpoint

The primary safety endpoint (PSE) is defined in **Section 3.3**.

The expected safety event rate for the PSE has been estimated by performing a meta-analysis on recently completed studies (see **Table 8.1-1**).

The selection of the studies eligible for the meta-analysis for safety was based on the following criteria:

- Prospective studies either single cohort or randomized trials with only large sample size (N>100), high quality, multi-center.
- Patients with PersAF: Studies with PAF or long-standing PersAF were excluded from the analysis. Also, studies with mixed population (i.e., including both PersAF and other forms of AF) were excluded if the safety results were not presented for PersAF subset only.
- Patients undergoing transcatheter ablation of AF, with approved energy source (e.g., radiofrequency, cryoballoon, laser). Studies that included any other concomitant treatment, surgical or trans-catheter (e.g., LAA closure, surgical ablation) were excluded.
- Collection of procedure-related serious adverse events had to be identified as an endpoint in the study (indicated as primary, secondary, or additional in the methods section of the paper, into SSED or supplementary material) and adequately reporting all the components of the safety endpoint were included in the ADVANTAGE AF protocol Phase 2 (i.e.: Death, Myocardial infarction, Stroke, TIA, Peripheral or organ thromboembolism, Pulmonary

edema, Unresolved phrenic nerve palsy / paresis, Vascular access complications , Heart block, Gastric motility / pyloric spasm disorders, Cardiac tamponade / perforation, pericarditis, PV stenosis and Atrio-esophageal fistula). The timeframe of reporting had to be at least 7 days post-procedure (i.e., peri-procedural events).

The analysis included 6 studies: event rates and their 95% confidence intervals were estimated from SSED, primary publications or results disclosed on clinicaltrials.gov and calculated based on the occurrence of the events that constitute the PSE defined in this protocol.

Table 8.1-1: Meta-Analysis to Determine Primary Safety Endpoint Parameters

Study	Design Info.	Technology	Event / Total	Rate (%)	95% CI
PRECEPT Trial	IDE, Prospective, multicenter, PersAF	RF with THERMOCOOL SMARTTOUCH SF catheter (PVI)	18/344	5.23	(3.13, 8.14)
CRYO4PERSISTENT AF	Prospective, multicenter, single arm, PersAF	Arctic Front Advance Cryo (PVI)	4/101	3.96	(1.09, 9.83)
Schmidt et al., 2017	Randomized, multicenter, PersAF	Laser Balloon vs. RF (PVI WACA)	7/134	5.22	(2.13, 10.47)
Wynn et al., 2016, SWAN-PAF	Prospective, multicenter, randomized, PersAF + sustained PAF	PVI vs. PVI + lines	8/124	6.45	(2.83, 12.32)
REAFFIRM Trial	Randomized, PersAF	RF (PVI vs. PVI+ FIRM)	25/350	7.14	(4.68, 10.36)
STOP Persistent AF Trial	IDE Prospective, PersAF	Cryo (PVI)	5/165	3.03	(0.99, 6.93)
*PersAF - Persistent AF, CFS- Contact Force-Sensing, PVI -pulmonary vein isolation					
Overall				5.41	(4.21, 6.75)
* Overall Rate, 95% CI calculated using a binary random effects model					

All events reported in the meta-analysis had an onset date <30 days after the ablation procedure and will therefore be considered as supportive data for formulation of an endpoint assessment of Day 90.

The overall safety event rate from this meta-analysis is 5.41%. We conservatively chose the expected rate of 6% based on potential unknown factors:

- (1) ablation includes both the posterior ablation wall and PVI ablation, a technique not commonly utilized in the studies listed above.
- (2) the FARAPULSE PFA System is different from those of listed studies in which either Cryoballoon ablation or RF ablation or other ablation systems were utilized.

The PSE performance goal of 12% was chosen based on the approximate upper limit of each individual study from the above analysis and deemed reasonable with an absolute difference of 6% from the expected rate 6%. The absolute difference is comparable to meaningful clinical difference of 8% used in both IDE single arm trials ((STOP Persistent AF trial²³ with performance goal 13% and (PRECEPT Trial²² with performance goal 16%).

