3.2 Primary Safety Endpoint

The primary safety endpoint (PSE) is the proportion of Treatment Subjects and Attempt Subjects with one or more of the following device or procedure-related Composite Serious Adverse Events (CSAEs) following the Index Procedure / Rescheduled Index Procedure or the Re-Ablation Procedure within the Blanking Period, with an Onset Date following the procedure as specified in **Table 3.2-1**:

Table 3.2-1: Primary Safety Endpoint Composite Serious Adverse Events

Composite Serious Adverse Events	Onset Date

 • Death • Myocardial infarction • Stroke • TIA • Peripheral or organ thromboembolism • Pulmonary edema • Unresolved phrenic nerve palsy / paresis • Vascular access complications • Heart block • Gastric motility / pyloric spasm disorders 	Day 0 – Day 7

 • Cardiac tamponade / perforation • Pericarditis 	Day 0 – Day 30

 • PV stenosis • Atrio-esophageal fistula 	Day 0 – Day 360 Assessment

For the analysis of the PSE, CSAEs are only defined for the following procedures that include the use of investigational devices:

- The Index Procedure / Rescheduled Index Procedure (**Section 7.6.1**)
- A Re-Ablation Procedure for AF, AFL or AT within the Blanking Period (**Section 7.13.1**)

Device or procedure-related SAEs related to any other ablation procedure that does not include an investigational device will not be included in the analysis of the PSE, including Other Re-ablation Procedures (**Section 7.13.2**).

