3.3 Primary Safety Endpoint

The primary safety endpoint (PSE) is the proportion of Treatment Subjects and Attempt Subjects with one or more of the following device or procedure-related Composite Serious Adverse Events (CSAEs) assessed through Day 90 following the Index Procedure / Rescheduled Index Procedure or the Re-Ablation Procedure on or prior to the Day 90 Assessment, with an Onset Date following the procedure as specified in **Table 3.3-1**.

Table 3.3-1: Primary Safety Endpoint Composite Serious Adverse Events

Composite Serious Adverse Events	Onset Date

 • Myocardial infarction • Stroke • Transient Ischemic Attack (TIA) • Peripheral or organ thromboembolism • Pulmonary edema • Unresolved phrenic nerve palsy / paresis • Vascular access complications • Heart block • Gastric motility / pyloric spasm disorders 	Day 0 – Day 7

 • Death • Cardiac tamponade / perforation • Pericarditis • Any PFA system related PFA procedure-related cardiovascular or pulmonary adverse event 	Day 0 – Day 30

 • PV stenosis • Atrio-esophageal fistula 	Day 0 – Day 90

For the analysis of the PSE, CSAEs are only defined for the following procedures that include the use of investigational devices:

- The Index Procedure / Rescheduled Index Procedure (**Section 7.7**)
- A Re-Ablation Procedure for AF, AFL or AT on or prior to the Day 90 Assessment (FARAWAVE only) (**Section 7.14**)

Device or procedure-related SAEs related to any other ablation procedure that does not include an investigational device will not be included in the analysis of the PSE, including those from Other Re-ablation Procedures (**Section 7.14.2**).

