Peripheral or organ thromboembolism	A cardiac thrombus that occludes a more distal arterial site other than the central nervous system (see Stroke). Cutaneous petechiae are excluded from this definition.

Related SAE	Description / Criteria
Cardiac tamponade / perforation	The development of a pericardial effusion post-ablation that results in hemodynamic compromise, requires pericardiocentesis or results in a 1-cm or more pericardial effusion as documented by echocardiography. Cardiac tamponade / perforation should also be classified as “early” or “late” depending on whether it is diagnosed during or following initial discharge from the hospital.
Pericarditis	The development of pericardial inflammation post-ablation that results in an effusion that leads to hemodynamic compromise or requires pericardiocentesis, prolongs hospitalization by more than 48 hours, requires hospitalization, or persists for more than 30 days following the ablation procedure.
Death	AE resulting in subject death; any subject death that occurs within 30 days of an ablation procedure with the FARAPULSE PFA System will be considered as device or procedure related unless proven otherwise and adjudicated as not related to the FARAPULSE PFA System or ablation procedure by the Clinical Events Committee.
Pulmonary edema	Respiratory compromise resulting from cardiac dysfunction or volume overload, leading to increased interstitial lung fluid requiring intubation or parenteral diuretics.
Vascular access complications	Vascular access complication (e.g., groin hematoma, AV fistula, pseudoaneurysm) requiring a significant and invasive intervention (e.g., surgical repair, blood transfusion or thrombin injection).
Heart block	Impairment of AV conduction that is related to a protocol-stipulated cardiac ablation procedure and that requires permanent pacing.
Gastric motility / pyloric spasm disorders	Evidence of impaired gastric motility or pyloric spasm that prolongs hospitalization, requires hospitalization, or persists for more than 30 days.
PFA system or procedure related cardiovascular or pulmonary event	Any PFA system-related or procedure-related cardiovascular or pulmonary adverse event that occurs within 30 days of an ablation procedure with the investigational device and prolongs or requires hospitalization > 48 hours (excluding AF, AFL, and AT).

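### Does the 88% power for the Phase 2 safety endpoint rest on a meta-analysis of a different composite?

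*Combined protocol and SAP*

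**What the plan says.** Appendix A section 8.1.1 derives the expected Phase 2 safety rate from six studies. To be eligible, a study had to be "adequately reporting all the components of the safety endpoint were included in the ADVANTAGE AF protocol Phase 2", and a parenthesis then names 14 components. The section adds that "The timeframe of reporting had to be at least 7 days post-procedure". The rates are described as "calculated based on the occurrence of the events that constitute the PSE defined in this protocol". The pooled rate is 5.41% (95% CI 4.21 to 6.75), raised to 6% for two reasons: posterior wall ablation and a different ablation system.

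The Phase 2 endpoint itself is set in Appendix A section 3.3. It is "assessed through Day 90 following the Index Procedure / Rescheduled Index Procedure", and Table 3.3-1 includes "Any PFA system related PFA procedure-related cardiovascular or pulmonary adverse event" with onset to Day 30. Table 3.3-2 limits that component to events that prolong or require hospitalization beyond 48 hours, and excludes the atrial arrhythmias under treatment. For a death within 30 days, Table 3.3-2 says it "will be considered as device or procedure related unless proven otherwise".

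Table 8.1-2 and the synopsis give an expected rate of 6%, a goal of 12%, 5% attrition, one-sided 0.025, 88% power, 245 evaluable and 258 enrolled.

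**The concern.** A list that claims to give every component of the Phase 2 endpoint omits one of them. The 14 items are those of Phase 1 section 8.1.1, in the same order. The six counts, the pooled rate and both reasons for moving to 6% are unchanged as well. Neither reason concerns the endpoint, so none of the 0.59 points between 5.41% and 6% is set aside for its change.

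The added component overlaps others but is not contained in them. About 30% of Treatment Subjects are expected to receive FARAPOINT, and Appendix A section 16.4 says its use may raise the risk of coronary spasm. A related spasm with a stay beyond 48 hours that missed the infarction criteria would count only under the new component.

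Safety sets the sample size. If the true Phase 2 rate were above 6%, the chance of passing would be below the printed 88%, and a reader of section 8.1.1 would not be warned.

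**Working it through.** **1. The two composites side by side** (Phase 1 Table 3.2-1; Appendix A Table 3.3-1)

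| Item | Phase 1 | Phase 2 | Possible effect on rate |
|---|---|---|---|
| Number of components | 14 | 15 | |
| Related cardiovascular or pulmonary event | absent | to Day 30 | up or none |
| Death | to Day 7 | to Day 30 | up or none |
| PV stenosis, atrio-esophageal fistula | "Day 0 – Day 360 Assessment" | to Day 90 | down or none |
| Other 11 components | as listed | same windows | none |

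The changes do not all point one way. Appendix A section 8.1.1 also states that every event in the meta-analysis began within 30 days of ablation, so cutting the last window to Day 90 takes nothing out of the pooled counts.

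**2. The pooled rate**

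Inputs (Table 8.1-1): 18/344, 4/101, 7/134, 8/124, 25/350, 5/165; total 67/1218.

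Arcsine square-root scale, DerSimonian-Laird: y = arcsin√(e/N), variance 1/(4N). The between-study variance is 0, so the pooled value is 0.2348 with SE = 1/√(4 × 1218) = 0.01433.

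- Rate: sin²(0.2348) = 5.41%
- Limits: sin²(0.2348 ± 1.96 × 0.01433) = 4.21% and 6.75%

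These are the printed figures.

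**3. The stated power**

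Inputs (Table 8.1-2): n = 245, goal 12%, one-sided 0.025.

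- P(X ≤ 19 | 245, 0.12) = 0.0211; P(X ≤ 20 | 245, 0.12) = 0.0351. The test passes at 19 or fewer subjects with an event.
- P(X ≤ 19 | 245, 0.06) = 0.898, against 88% stated.
- Attrition: 258 × 0.95 = 245.1.

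The planned log-log limit gives the same cut when nobody is censored. For 19/245: S = 0.92245, −ln S = 0.08072, SE of ln S = √(19/(245 × 226)) = 0.01852, and 0.01852/0.08072 = 0.2295. The upper limit is 1 − S^exp(1.96 × 0.2295) = 11.89%, a pass. For 20/245 it is 12.37%, a fail.

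**4. How far the 88% reaches** (n = 245, pass at 19 or fewer)

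| True rate | Exact power | Source of the rate |
|---|---|---|
| 5.41% | 95.5% | pooled estimate |
| 6% | 89.8% | plan |
| 6.14% | 88.0% | solved for 88% |
| 6.5% | 82.5% | assumed |
| 6.75% | 78.0% | upper limit of pooled CI |
| 7% | 73.0% | assumed |

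In subjects: 0.06 × 245 = 14.7 expected with an event. One more (15.7/245 = 6.41%) gives 84.0%; two more (16.7/245 = 6.82%) give 76.7%. The 0.59-point margin over the pooled rate is 0.0059 × 245 = 1.4 subjects.

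The 6.5% and 7% rows are illustrations. The 6.75% row reflects sampling error in the pooled rate and has nothing to do with the added component.

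**5. What the documents leave open**

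The 14-item list sits in the study-eligibility criterion. The counting rule is a separate sentence. Unchanged counts fit either of two histories: the six studies were not re-read, or they were re-read and no further subject was found. The documents do not say which.

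**The case for a change.** The strongest case for a change is that the list is wrong as written and that the endpoint driving 258 subjects deserves a rate shown to match it. The sentence on onset within 30 days answers the timing question only. Selection required as little as 7 days of reporting, so capture of 30-day hospitalizations is not assured. The FARAPOINT feasibility evidence is thin: no clinical sign of spasm in 20 subjects still allows a one-sided 95% upper limit of 1 − 0.05^(1/20) = 13.9%. Power is also steep in the rate, as the table shows, and a corrected list with a power-by-rate note would cost only wording.

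The omission stands. The proposed remedies add little:

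- Saying that 5.41% covers only the 14 Phase 1 components would assert something the documents do not settle.
- Marking the 88% as conditional on 6% repeats what Table 8.1-2 and the synopsis already print, since both present the 6% as an assumption.
- A table at higher rates would suggest an effect size that nobody has estimated.
- The spasm route is narrow. Table 3.3-2 already counts as infarction any new ischemic ECG change lasting over an hour and any new regional wall motion abnormality.
- Appendix A section 4.3 already tells the reader that Phase 2 safety uses the Phase 1 assumptions.

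**Conclusion.** No change to the plan is needed. The list in Appendix A section 8.1.1 is incomplete, most simply read as text carried over from Phase 1, and the documents do not show whether the added component was counted. That is a gap in the background to a planning assumption. Events in the trial will be classified by Tables 3.3-1 and 3.3-2 with committee adjudication, not by the meta-analysis list, so the slip cannot alter the result.

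No figure is shown to be wrong. Exact power at the plan's 6% is 89.8%, slightly above the 88% stated, and 88% holds to about 6.14%. If the wider composite did raise the rate, the cost would be a lower chance of passing, borne by the sponsor. The test against 12% would keep its exact type I error of 2.1%, and holding a wider composite to the same goal makes the test harder to pass, not easier.

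This rests on 245 evaluable subjects, the exact binomial without censoring, and the absence of any documented rate for the added component. The powers at 6.5% and 7% are illustrations, not forecasts.
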